Biopsies obtained without the use of EMN or SSCB (e.g., sampling of central lymph nodes using the linear endobronchial ultrasound bronchoscope) will not be included in the diagnostic yield calculations. In case of repeat bronchoscopies, only the index bronchoscopy will be included in the diagnostic yield calculation.

Secondary Outcomes

There is one secondary outcome for the trial, which will be collected during the bronchoscopy procedure.

a) Duration of procedure (in minutes), defined as time from the start of airway registration to

the removal of the bronchoscope after completion of navigation procedures.

Exploratory Endpoint(s)

There are three exploratory endpoints that are prespecified. These can be collected during and immediately after the bronchoscopy procedure, and/or during the follow-up period.

a) Need for additional diagnostic procedures. Any diagnostic procedure performed within 12 months of the study bronchoscopy that targets the same peripheral lesion (including repeat bronchoscopy, transthoracic needle biopsy, or surgical lung biopsy) will be considered an additional diagnostic procedure.

1. Repeat biopsies of lesions determined to be malignant by study bronchoscopy which are 1) performed specifically to obtain additional tissue for further testing but that does not change the malignant diagnosis, or 2) therapeutic surgical resection of such lesions, will not be considered additional diagnostic procedures.

b) Radiation exposure, defined as radiation dose delivered to the patient during the study bronchoscopy, recorded as a dose area product (mGy/cm2).

Diagnostic accuracy

Diagnostic accuracy will be assessed for the two devices. Lesions will be categorized as positive (malignant) lesions or negative (specific benign diagnosis). The criterion standard for a negative diagnosis will be no evidence of malignancy at 12-month follow-up (no interval biopsy diagnostic of malignancy, regression on CT or stable size with no plan for repeat diagnostic procedure).

Safety outcome

The main safety outcome for this trial is occurrence of procedure complication(s), defined as the occurrence of any of the following: respiratory failure, pneumothorax, anesthetic complications, and bronchopulmonary hemorrhage.

Safety outcomes will be reported overall and by type.

Statistical analysis plan for **R**obotic versus Electromagnetic Bronchoscopy for Pulmonary LesIon Assessme**NT**: the RELIANT trial PI: [name]

Analysis dataset

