The analysis for the trial will use a intent-to-treat approach. Participants will be evaluated by treatment group as assigned regardless of what was delivered; participants will be excluded if their procedure did not begin, defined as the start of the navigation procedure itself. All eligible participants will be included.

The safety analysis dataset will group participants by device used, regardless of assignment.

Statistical Approach

Our initial analysis will be descriptive in nature, summarizing information that characterizes the cohort and the outcomes. Then, we will proceed with inferential analysis. No interim analyses are planned.

Descriptive Analysis

To characterize the study sample, baseline demographic and clinical data will be described overall and by group. Categorical variables will be described using frequencies and proportions, and continuous variables will be described using means and standard deviations or medians and interquartile ranges, as appropriate. Missingness will be reported for each variable. At a minimum, the following variables will be described at time of enrollment:

- Age (years)
- Gender (male, female, unknown)
- Race (African American, Asian/Pacific Islander, Caucasian, Multiple, Native American, Other, Unknown)
- Ethnicity (Hispanic, Non-Hispanic, Unknown)
- History of cancer (yes/no)
- Smoking History (current, former, never)
- Body mass index (BMI)
- Lesion characteristics
 - o Size (mm)
 - Location (middle vs peripheral)
 - Upper lobe (yes/no)
 - Density (solid, part solid, ground glass opacity)
 - Distance from pleura (cm)
 - Bronchus sign present (yes/no)
- Procedure details

Statistical analysis plan for **R**obotic versus Electromagnetic Bronchoscopy for Pulmonary LesIon AssessmeNT: the RELIANT trial PI: [name]

PI: [name]

- Rapid onsite evaluation (yes/no)
- o Operator
- Digital tomosynthesis (yes/no)
- Cone beam computed tomography (yes/no)
- Biopsy tools

We will describe the outcome variables overall and grouped by study arm using the same approach as for the demographic data. Summary statistics and graphical representations may be displayed, and missingness will be reported for each variable. No statistical comparisons between groups will be done for this descriptive analysis.

Primary analysis

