The primary analysis for the trial will use an intent-to-treat approach. Participants will be evaluated by treatment group as assigned regardless of what was delivered. All eligible participants will be included.

The primary outcome variable (diagnostic yield) will be compared between groups using a generalized linear mixed model with one-sided test. The primary model will be covariate adjusted, including fixed effects for device assignment, lesion size, density, peripheral location, and bronchus sign, and a random effect for operator. Should the model demonstrate signs of overfitting, covariates may be selected based on priority order (device assignment, lesion size, density, peripheral location, sign, operator).

If non-inferiority is demonstrated, we will proceed with a superiority analysis using the same approach as the non-inferiority analysis, an adjusted generalized linear mixed effects model with the same covariates used in the primary analysis. No adjustment will be made for multiplicity. The superiority analysis would be conducted at a one sided p-value of 0.05.

Secondary and exploratory analysis

A sensitivity analysis using a *per protocol* approach will be conducted to analyze participants based on the device used. We will use the same approach as the primary analysis, an adjusted generalized linear mixed effects model using the same covariates.

The secondary outcome, procedure duration, will be compared between study groups using a linear mixed model. If the procedure duration is skewed, alternative models may be pursued,

Statistical analysis plan for **R**obotic versus Electromagnetic Bronchoscopy for Pulmonary LesIon AssessmeNT: the RELIANT trial PI: [name] such as a cox regression. The primary model will be covariate adjusted following a similar approach to the analysis of the primary outcome. Analysis of the exploratory endpoints will follow a similar approach.

Safety analysis

Procedure complications are expected in usual care, although uncommon. We will report all procedure complications for each device, overall and by type. If event rates exceed 5%, we may proceed with a comparative analysis, which will involve a generalized linear mixed regression model for binary outcomes as specified for the main analysis, with the exception that covariate adjustment may not be possible. The safety analysis dataset will group participants by device used, regardless of assignment.

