All model results will be summarized with point estimates and 95% confidence intervals (CIs), which will be emphasized over p-values when reporting the results for secondary outcomes. No adjustments for multiplicity will be made.

Differential effects

To determine whether differences in outcomes are dependent on baseline characteristics, we will introduce interaction terms into the models developed for the main analysis. Specifically, we will test the interaction between device assignment and the subgrouping variable. Each variable will be tested one by one, such that all main effects but only one interaction term is included at a time. The following putative subgrouping variables are prespecified:

- Nodule size (continuous, treatment effects will be estimated at 1.5cm and 3cm)
- Presence of bronchus sign
- Solid vs subsolid nodule
- Peripheral vs central location Peripheral defined as outer 1/3 of chest

Missingness on the primary or secondary outcome is not expected due to the proximity of its measurement with the procedure and its integration into clinical documentation. Procedures missing the primary outcomes will be considered not diagnostic. Missing covariates will be imputed using multiple imputation with predictive mean matching. There may be missingness on exploratory outcomes. For missing exploratory outcomes, a complete case analysis will be performed.

Statistical analysis plan for Robotic versus Electromagnetic Bronchoscopy for Pulmonary LesIon AssessmeNT: the RELIANT trial

PI: [name]

Diagnostic accuracy

Diagnostic test statistics (e.g., sensitivity, specificity, predictive values, likelihood ratios) will be reported for the two devices. In addition, accuracy of the diagnosis may be modeled using a generalized linear model to explore whether participant or lesion features are predictive of procedure success, as described for the differential effects analysis.

Summary

The results of this study will help to determine whether there is a difference between these two diagnostic bronchoscopy platforms for patient outcomes. The analysis approach we describe is selected based on the trial's pragmatic nature and specifically the intent to understand if the diagnostic yield of the IonTM Endoluminal System (SSCB) is not inferior to the ILLUMISITETM Platform (EMN) in patients undergoing bronchoscopy to biopsy a peripheral lung lesion.

Version and Revision Log

7/12/2022	Version 1: developed with and approved by [name].

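### The radiation-dose model takes over the covariates chosen for diagnostic yield and leaves out BMI, a listed baseline variable; the likely cost is a modest loss of precision on an exploratory endpoint

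*SAP*

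**What the plan says.** The Protocol (Objectives) names radiation exposure among the comparisons between platforms. The Protocol (Exploratory outcomes) and the SAP (Exploratory Endpoint(s)) class it as exploratory, recorded as a dose area product.

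The SAP (Secondary and exploratory analysis) gives the model by cross-reference only: "Analysis of the exploratory endpoints will follow a similar approach". The sentences before it concern procedure duration:

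- Model: "The secondary outcome, procedure duration, will be compared between study groups using a linear mixed model".
- Skewness: "If the procedure duration is skewed, alternative models may be pursued", with Cox regression given as an example.
- Covariates: "The primary model will be covariate adjusted following a similar approach to the analysis of the primary outcome".

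The SAP (Primary analysis) defines that covariate set as "including fixed effects for device assignment, lesion size, density, peripheral location, and bronchus sign, and a random effect for operator".

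BMI appears in the SAP (Descriptive Analysis), in the list of variables to be described at enrolment. It appears in no model. Missing covariates are to be multiply imputed (SAP, end of Differential effects). For missing outcomes of this class the rule is: "For missing exploratory outcomes, a complete case analysis will be performed".

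**The concern.** The four lesion covariates make sense for diagnostic yield, because they describe how hard a lesion is to reach and sample. Dose area product is a different kind of outcome. It plausibly depends on body size, since a thicker chest generally needs more X-ray output to image. That is general reasoning about imaging; neither document states it.

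The inherited set contains no measure of body size, yet the trial already lists one at baseline. BMI precedes the procedure and device assignment cannot affect it, so it is a safe adjustment variable. Use of tomosynthesis or cone beam CT, which the SAP lists among the procedure details, is different: adjusting for it could remove part of the device effect.

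What is at stake is the width of the interval for the platform difference in dose. If BMI predicts dose, a model without it leaves explainable variation in the residual.

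**Working it through.** **The plan's own figure.** No precision or power is stated for radiation exposure. The only power figure for the planned sample size is for the primary test: 0.80327 with 2 × 101 = 202 per arm (Protocol, sample size table; yield 80% in both arms, margin 10 points, one-sided 5%, intracluster correlation 0). It reproduces with the Farrington-Manning score test:

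- Constrained proportions under the null, 0.10 apart: 0.7411 and 0.8411.
- Null standard error: √[(0.7411 × 0.2589 + 0.8411 × 0.1589)/202] = 0.04015.
- Alternative standard error: √(2 × 0.8 × 0.2/202) = 0.03980.
- Power: Φ[(0.10 − 1.645 × 0.04015)/0.03980] = 0.8033.

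This confirms 202 per arm as the planning size. It says nothing about dose.

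**Which covariates the dose model gets.** Following the cross-references, exploratory endpoints follow the duration analysis, and duration follows the primary-outcome adjustment. The primary adjustment is device, lesion size, density, peripheral location and bronchus sign, with a random operator effect. BMI is not in that chain.

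**Inputs for the size of the loss.**

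- n = 202 per arm (Protocol, Sample Size Calculation; SAP, Sample Size Considerations).
- 95% confidence intervals for all models (SAP, Safety analysis, closing paragraph).
- Partial correlation r between BMI and dose, given the other covariates: not in the documents. Assumed range 0.2 to 0.5.
- Residual standard deviation of dose: not in the documents, so half-widths are in units of that SD.
- Independent observations and complete data are assumed. Clustering or missing doses would widen the intervals both with and without BMI.

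**Formulas.** Half-width without BMI = 1.96 × √(2/202) = 0.195 SD. With BMI it is multiplied by √(1 − r²). The equivalent gain in sample size is 1/(1 − r²) − 1.

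| Assumed r | √(1 − r²) | Half-width (SD) | Interval narrower by | Equivalent gain in n |
|---|---|---|---|---|
| 0.2 | 0.980 | 0.191 | 2.0% | 4% |
| 0.3 | 0.954 | 0.186 | 4.6% | 10% |
| 0.4 | 0.917 | 0.179 | 8.3% | 19% |
| 0.5 | 0.866 | 0.169 | 13.4% | 33% |

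At r = 0.1 the gain is 0.5%, which is negligible.

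**Bias or precision.** Chance BMI imbalance between arms has a standard deviation of √(2/202) = 0.0995, about 0.10 of a BMI SD. That imbalance is the mechanism behind the precision loss in the table and is already reflected in the unadjusted interval. It is neither a second harm nor a systematic bias.

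**Scale of the outcome, as a side calculation.** If dose were lognormal with log-scale SD s (assumed), the coefficient of variation would be √(exp(s²) − 1). The relative standard error on the log scale would then be lower than on the raw scale by 1 − s/CV:

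- s = 0.4: CV 0.42, 4% lower.
- s = 0.6: CV 0.66, 9% lower.
- s = 0.8: CV 0.95, 16% lower.
- s = 1.0: CV 1.31, 24% lower.

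This would count against the plan only if it fixed the raw scale, and it does not.

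**The case against.** **The endpoint is exploratory and the gain may be small.** No power claim, margin or decision rule rests on radiation exposure, and one covariate set across outcomes is a defensible choice made in advance. The link between BMI and dose is not in the documents. Imaging mode may account for much of the variation in dose, since tomosynthesis is built into the EMN platform and its use, like that of cone beam CT, is listed as a procedure detail; that would shrink BMI's share. All of this stands, and it limits the size of the point. It does not remove the point, because the covariate is already listed and adding it is nearly free.

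**A stronger reading: the SAP commits dose to an untransformed linear model, with Cox regression as the fallback.** A reader might infer this, and conclude that the result will be dominated by a few high-dose procedures or reported only as a hazard ratio. The text does not support it. The cross-reference asks only for a similar approach, the duration template allows other models when data are skewed, and Cox regression is an example written for duration. The SAP (Descriptive Analysis) also has every outcome summarised by arm, so dose will be shown in its own units whatever the model.

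**A second stronger reading: omitting BMI leaves an uncorrected imbalance that distorts the comparison.** Under random allocation this is the precision loss already counted, not bias.

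**The log scale is not a free improvement.** A geometric mean ratio and a difference in arithmetic means answer the same question only if log-scale variance is equal in the two arms. Log dose is also undefined at zero, so a log-scale main model could drop patients on the basis of an outcome measured after allocation. That is why a log model is only an option here.

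**Conclusion.** The point holds as a minor one. On the plain reading of the SAP, the radiation-dose model uses covariates selected for diagnostic yield and omits BMI, which is listed at baseline and plausibly predicts dose. The loss is one of precision: about 2% to 13% of confidence-interval width for an assumed partial correlation of 0.2 to 0.5 at 202 per arm, and close to nothing if the correlation is nearer 0.1. The estimate rests on that assumed correlation, independent observations and complete dose data. The scale, the trigger for changing model and the effect measure are left open for dose. That is worth tidying but is not an error in the plan.

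**What to change.** In the SAP (Secondary and exploratory analysis), add a sentence for radiation exposure: the mixed model uses the primary-model covariates and the random operator effect, plus BMI (continuous) as a fixed effect, and missing BMI is handled by the multiple imputation already planned for covariates.

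The cost is one model parameter, negligible at about 404 patients (2 × 202), and a line of SAP text to be settled before unblinding. BMI is already listed at baseline, so no new data item is needed.

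As a secondary suggestion, the same sentence could say what happens if dose is skewed. A mixed model on log dose, reported as an SSCB-to-EMN ratio of geometric means with its 95% confidence interval, keeps the result in dose terms. If that route is taken, the SAP should also say how procedures with zero recorded dose stay in the main comparison.

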# **Objectives**

This is an investigator-initiated, non-inferiority, open labeled, cluster randomized controlled trial. Our primary objective is to compare the diagnostic yield of the IonTM Endoluminal System (SSCB) to the ILLUMISITETM Platform (EMN bronchoscopy) in patients undergoing bronchoscopy for PPL evaluation. Our secondary objective is to compare the rate of complications, procedure time, radiation exposure, absence of malignancy at 12 months, and need for additional procedures between these two bronchoscopic modalities.

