## **Procedure Related Risks**

The procedures being studied are considered standard of care and are being undertaken for routine care of the patient. As such, we do not expect that enrollment in this study will result in an increased risk for the patient above what they are experiencing as part of their routine care. The risks of navigational bronchoscopy for the biopsy of PPLs are well defined, and include pneumothorax, bronchopulmonary hemorrhage, which could result in the need for a blood transfusion, respiratory failure, and anesthetic complications. Risk of death is estimated around 1/10,000. Pneumothorax is the most common complication, occurring in approximately 2% of cases in a large prospective multicenter study (3) and may result in the need for a chest tube. Existing data for SSCB indicates a similar risk profile, which also underlie its recent FDA clearance via 510(k) pathway which requires a demonstration of similar risk to a predicate approved or cleared device. Procedural risks are collected in the CRF and may be reviewed by the DSMB. As these are considered procedural risks and not research related risks, they will not be reported to the IRB.

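### Comparing complication rates is a stated objective, but the SAP makes it optional and subject to an undefined 5% event-rate condition, so no between-device difference or interval is guaranteed

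*SAP*

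**What the plan says.** Protocol, Objectives: "Our secondary objective is to compare the rate of complications, procedure time, radiation exposure" and other outcomes. The protocol's Statistical Analysis Plan section assigns additional between-group comparisons to a mixed model and attaches no event-rate condition.

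SAP, Safety outcome: the main safety outcome is a composite, the "occurrence of any of the following: respiratory failure, pneumothorax, anesthetic complications, and bronchopulmonary hemorrhage".

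SAP, Safety analysis: complications are always reported for each device, overall and by type. A between-device comparison is a separate and conditional step: "If event rates exceed 5%, we may proceed with a comparative analysis". It would be a binary mixed model, possibly without covariates.

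SAP, text following the safety analysis: "All model results will be summarized with point estimates and 95% confidence intervals (CIs"). The SAP's Descriptive Analysis section says that no statistical comparison between groups belongs to the descriptive step.

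Protocol, Procedure Related Risks: "Pneumothorax is the most common complication, occurring in approximately 2% of cases in a large prospective multicenter study (3"). For the robotic platform it gives no figure, only that "Existing data for SSCB indicates a similar risk profile". Neither document gives an expected rate for the composite.

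**The concern.** The objective is unconditional, but the analysis that serves it is not. Three features of the SAP sentence matter.

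- It depends on the observed data.
- It is permissive even when the condition is met.
- It leaves the event rate undefined: pooled or per device, composite or by type. That choice would be made with the results in view, in an open-label trial.

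Nothing replaces the comparison when it is not made. The descriptive step excludes comparisons, and intervals are tied to models. A report could therefore show two columns of counts and percentages with no effect estimate. Some readers would take the missing comparison as reassurance that the devices are equally safe.

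**Working it through.** **Inputs.** 202 per arm, 404 in total (both documents, sample size sections); threshold above 5% (SAP, Safety analysis); 2% for pneumothorax alone (Protocol, Procedure Related Risks). Composite rates above 2% are assumptions. If pneumothorax is the most common of the four components, the composite lies between about 2% (complete overlap) and 4 × 2% = 8% (four equally common components, no overlap). Procedures are treated as independent.

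**Plan's own figure.** The documents state no power for safety. The only figure to reproduce is the primary power of 0.80327 with 202 per arm (80% versus 80%, margin 10 points, one-sided 5%, ICC 0). The Farrington-Manning null proportions are 0.8411 and 0.7411.
- Null SE = √[(0.8411×0.1589 + 0.7411×0.2589)/202] = 0.04015
- Alternative SE = √[2×0.8×0.2/202] = 0.03980
- Power = Φ[(0.10 − 1.645×0.04015)/0.03980] = Φ(0.853) = 0.8033, which agrees.

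**Events needed to exceed 5%.** Pooled: 0.05×404 = 20.2, so at least 21 events. One arm: 0.05×202 = 10.1, so at least 11 events.

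**Chance that the condition is met.** Pooled = P(X ≥ 21), X ~ Bin(404, p). Either arm = 1 − [1 − P(Y ≥ 11)]², Y ~ Bin(202, p).

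| True rate, both arms | Pooled | One given arm | Either arm |
|---|---|---|---|
| 2% | 0.009% | 0.27% | 0.55% |
| 3% | 1.2% | 4.3% | 8.3% |
| 4% | 13.6% | 18.8% | 34.1% |
| 5% | 45.9% | 43.0% | 67.5% |
| 6% | 78.0% | 67.2% | 89.2% |
| 8% | 98.9% | 93.6% | 99.6% |

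With a true imbalance of 2% versus 6%, the condition is met in 13.5% of trials on the pooled reading and 67.3% on the either-arm reading. The undefined wording therefore changes the chance of a comparison about fivefold.

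**An imbalance that no reading catches.** Take 10/202 versus 2/202: 4.95% and 0.99%, pooled 12/404 = 2.97%. None exceeds 5%, and no single type can exceed the composite. The Newcombe interval combines the Wilson limits, 2.71% to 8.87% and 0.27% to 3.54%:
- Difference = 4.95 − 0.99 = 3.96 points
- Lower = 3.96 − √[(4.95−2.71)² + (3.54−0.99)²] = 0.57
- Upper = 3.96 + √[(8.87−4.95)² + (0.99−0.27)²] = 7.95

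The interval excludes zero, yet the plan commits to no estimate.

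**What an unconditional interval would give.** At 4/202 versus 4/202 the Wilson limits are 0.77% to 4.98% in each arm. The Newcombe half-width is √[(1.98−0.77)² + (4.98−1.98)²] = 3.2 points. That is wide, but it is a bound. Two-sided power at 5% is 37% for 2% versus 5% and 79% for 2% versus 8%.

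**The case against.** The strongest defence is that the condition guards against fitting a mixed model to very few events. At a 2% rate, about four events per arm are expected (0.02×202), and the SAP already allows that covariate adjustment may be impossible. The comparison is also unpowered, complications are a safety outcome rather than the SAP's single secondary outcome, and a DSMB reviews safety. All of this stands as a reason not to rely on a model. It is not a reason to withhold a difference and interval, which need no model. Low power makes an interval more useful, because it shows how large a difference remains possible.

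Two stronger readings are tempting, and the documents do not support either.

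- A reader might infer that the condition will almost never be met. That follows only for pneumothorax alone or a composite near 2%. The main safety outcome is a four-part composite with no stated rate, and at 5% or 6% the condition is met often.
- A reader might infer that the complication objective goes unanswered or that only raw counts are planned. The SAP always reports complications by device and by type, describes categorical outcomes by frequencies and proportions, and the protocol's Outcomes Definitions give the denominators. A reader could compute the difference. What is missing is a prespecified estimate with an interval.

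The 10 versus 2 example sits at the edge: ten is the largest count in an arm that does not exceed 5%, and with 11/202 (5.4%) a per-device reading would be met. It shows that the gap exists, not how often it would arise.

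**Conclusion.** The point holds as a mismatch between the objective and the committed analysis. The comparison is optional, its condition is undefined, and no between-device difference or interval is guaranteed if the model is not fitted. None of this depends on an assumed event rate.

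How often the gap would bite does depend on one. The condition is met in under 1% of trials at a true 2%, and in 14% to 89% at assumed composite rates of 4% to 6%, depending on the rate and on the pooled or either-arm reading. These probabilities and the intervals assume 202 per arm and independent procedures; clustering by OR-day and operator is ignored. The safety dataset groups by device used, so the actual denominators may differ somewhat. The primary non-inferiority conclusion and data collection are unaffected.

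**What to change.** In the SAP's safety analysis, remove the 5% condition for effect estimation. Commit to reporting, whatever the event rate, the between-device risk difference with a 95% score-type interval (Newcombe or Miettinen-Nurminen) for any complication and for pneumothorax, in the device-used dataset. State that these intervals treat procedures as independent, or add a cluster-robust check by OR-day where events allow. Keep the mixed model as an optional addition when events suffice, and define which rate governs that option. If the team prefers not to commit to an estimate, the protocol objective should be reworded as descriptive.

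The cost is a short SAP edit and one table, with no new data. The downside is wide intervals when events are rare, about ±3 points at 4 versus 4 events.
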